8.1.1 Demographics

Demographics and baseline characteristics will be summarized for all enrolled subjects by arm (Arm 1 and Arm 2) with further breakdown by categories of Arm 2 (2A, 2B and 2C), and overall. Baseline characteristics include age, weight, height, BMI, gender, race, ethnicity, cause of end-stage kidney disease, dialysis vintage, prior solid organ transplantation, liver fibroscan results, and any HCV treatment history (for participants previously cured of HCV infection) and match run position for kidney transplant recipients. For subjects in Arm 2B, further breakdown by the subgroups allowed in Arm 2B will be summarized - 2B1 to 2B5.

Donor variables will include donor age, sex, race, terminal serum creatinine, cause of death, PHS increased risk status, KDPI score, cold ischemia time, and where available, characteristics of the donor HCV including genotype.

Summary statistics (N, mean, median, SD, and range) will be generated for continuous variables (e.g., age and BMI), and the number and percentage of subjects will be presented for categorical variables (e.g., sex and race).

Study drug G/P exposure and compliance will be summarized for Arm 1. Treatment compliance to study drug will be calculated based on the percentage of tablets taken relative to the total tablets expected to be taken, where these data are available. A subject is considered to be compliant if the percentage is between 80% and 120%. Compliance will be calculated for each subject and summarized with the mean, median, standard deviation, minimum, and maximum. The percentage of compliant subjects will be summarized.

8.1.2 Efficacy

All efficacy analyses will be performed on the ITT population, unless otherwise specified. Plasma HCV RNA levels will be determined for each sample and measured using standard of care in the clinical site labs. HCV RNA \geq the lower limit of quantification (LLOQ) are all quantifiable values.

8.1.2.1 Primary Efficacy Endpoint

The primary efficacy endpoints is the proportion of ITT subjects who achieved SVR₁₂ (HCV RNA < LLOQ 12 weeks after the last actual dose of study drug).

The number and percentage of subject achieving SVR₁₂ will be summarized along with a two-sided 95% confidence interval calculated using Wilson's score method. A summary of reasons for SVR₁₂ non-response (e.g., on-treatment virologic failure, relapse, other) will be provided.

8.1.2.2 Secondary Efficacy Endpoints

The secondary efficacy endpoints to be summarized for all ITT subjects who are:

- the number and percentage of subjects with on-treatment virologic failure (confirmed increase of $> 1 \log_{10}$ IU/mL above nadir during treatment, confirmed HCV RNA ≥ 100 IU/mL after HCV RNA $<$ LLOQ during treatment, or HCV RNA \geq LLOQ at the end of treatment with at least 6 weeks of treatment);
- the number and percentage of subjects with post-treatment relapse (defined as confirmed HCV RNA \geq LLOQ between end of treatment and 12 weeks after the last dose of study drug among subjects who completed treatment as planned with HCV RNA $<$ LLOQ at the end of treatment, excluding subjects with reinfection).

For the analysis of relapse, completion of treatment is defined as any subject with study drug duration of 49 days or greater for 8-week treatment.

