All subjects who received at least one dose of study drug will be monitored during the post-transplantation period for safety, HCV RNA, and the emergence and persistence of resistance-associated viral substitutions for an additional 12 and 24 weeks following the last dose of G/P. For recipients of HCV RNA-positive transplants in Arm 1, a 1-year post kidney transplant visit is included to assess for graft function and survival, eGFR and proteinuria, and donor specific antibody (abstracted from the center's medical records), as applicable per the center's standard of care.

Appropriate information from original clinic notes, telephone notes, locally available safety labs/evaluations and/or diagnostic tests, or health screenings collected during the post-HCV treatment period will be abstracted at the clinical sites to identify and report adverse events, vital signs, physical examinations, concomitant medications, HCV RNA, HCV resistance, and clinical laboratory tests that were collected as part of standard of care practice.

The Post-Treatment Period will begin the day following the last dose of study drug treatment.

Subjects who prematurely discontinue treatment should return to the site for a Post-Treatment Discontinuation Visit as outlined in Tables [5](#) and [7](#) and will be followed for all post-treatment safety, HCV RNA, and resistance-associated substitutions according to the post treatment period schedule.

5.1.6.1 Post-treatment visits for subjects who receive an HCV RNA-positive kidney in Arm 1

Visit 9: Telephone encounter or in person visit (4 week after end of G/P treatment)

Visit 9 should occur 4 weeks after end of G/P treatment ± 7 days. Note that this visit can be performed as an in-person visit to the study site, if there is a standard of care post-transplant visit on the same date.

The following research procedures and activities will be performed

- Assess for Transplant-related, HCV-related, and study drug related Adverse Events, including clinical outcomes (same as described in Visit 3)
- Obtain medication data
- Confirm follow-up visits

Visit 10: (12 weeks after end of G/P treatment)

Visit 10 should occur 12 weeks after end of G/P treatment ± 14 days. If possible, it should immediately follow the subject's regularly scheduled post-transplant follow-up visit at the study site and will provide an opportunity to assess SVR12.

The following research procedures and activities will be performed:

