Day 1 of G/P treatment	V3	✓	✓								✓	✓	✓	✓	✓				
Treatment week 1 ±3 days	V4	✓	✓		✓			✓					✓	✓	✓				
Treatment week 2 ±3 days	V5 T5	✓	✓		✓														
Treatment week 4 ±3 days	V6	✓	✓		✓	✓		✓			✓	✓	✓	✓	✓	✓			
Treatment week 6 ±3 days ¹⁰	T7	✓	✓		✓														
Treatment week 8 ±7 days (EOT)	V8	✓	✓		✓			✓			✓		✓	✓	✓				
Post treatment week 4 ±7 days	V9 T9	✓	✓																
Post treatment week 12 ±14 days	V10	✓	✓					✓	✓										
Post treatment week 24 ±28 days	V11	✓	✓					✓	✓				✓	✓	✓				
1 year Post transplant ±28 days; End of study ¹¹	V12	✓	✓					✓	✓				✓	✓	✓				
G/P treatment failure		✓						✓	✓	✓									
Premature discontinuation		✓						✓	✓	✓			✓	✓	✓				

1 Visit types: V - in person visit to site; L - Lab visit; T - Telephone encounter

2 Includes evaluation of blood type and HLA compatibility

3 HCV RNA testing at V2, V4, V8, and V10 and V11 are study paid labs. HCV RNA testing at visit 6 is billed as SOC. All HCV RNA testing is done at local laboratory by a CLIA certified laboratory and with an FDA approved test.

4 Archived plasma samples (required) and PBMC (optional at Visits 8, 10, and 12) samples are shipped to the clinical coordinating center at Massachusetts General Hospital, see section 5.3.1.1

5 Lack of availability of donor blood sample will not preclude donor eligibility or transplant. HCV genotype is determined from the donor blood sample at local laboratory; Another portion of the donor sample is frozen for storage and potential testing for DAA resistance as needed. See section

5.3.1.1

6 If visit 2 and visit 3 are on the same day or within 14 days of each other only 1 serum pregnancy test need to be obtained. Visit 6 and Visit 8 pregnancy tests can be urine tests. Additional pregnancy tests not billed to the study are obtained as per transplant center standard of care.

7 Vitals and physical exam will be conducted and documented as per standard of care at transplant center

8 Liver function tests (ALT, AST, Alk Phos., total bilirubin) will be ordered as a study lab if not standard of care as part of clinical chemistry labs at the local transplant center. See table 8 for clinical chemistry labs and hematology labs.

9 Includes Tacrolimus level and/or other utilized immunosuppressant that requires therapeutic drug monitoring as per transplant center standard of care;

10 Telephone call will be performed between clinic visits at treatment week 6 to assess subject adherence to G/P treatment.

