5.4.1.1 Virologic Stopping Criteria

Individual patient

Virologic stopping criteria are defined as one of the following:

1. Confirmed HCV RNA \geq 100 IU/mL (defined as 2 consecutive HCV RNA measurements \geq 100 IU/mL) after HCV RNA $<$ LLOQ during treatment.
2. Confirmed increase from nadir in HCV RNA (defined as 2 consecutive HCV RNA measurements of $>$ 1 log₁₀ IU/mL above nadir) at any time point during treatment.

When confirmatory testing is required, it should be completed as soon as possible and the subject should remain on study treatment until the virologic stopping criteria has been confirmed. Subjects meeting virologic stopping criteria will be discontinued from study drug and will continue to be followed in the Post-Treatment Period for the emergence and persistence of resistant viral variants until 12 weeks post-treatment.

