5.5.1.1 G/P Initial Treatment Failures

Study subjects with treatment failure, defined as meeting virologic stopping criteria (Section 5.4.1.1) or virologic relapse (unquantifiable viral load after completion of treatment that during the post-treatment follow-up period becomes quantifiable) will be provided with either 1) Open-label Sofosbuvir + G/P ± Ribavirin or 2) Open-label sofosbuvir/velpatasvir/voxilaprevir +/- Ribavirin. The regimen will be chosen at the discretion of study's Principal Investigator ([name]), with input from the site investigator where the patient is located. The retreatment of study subject will be followed

by the site investigator and as per local center standard of care. Outcomes of HCV re-treatment will also be collected. AbbVie will provide G/P, and funds for purchasing sofosbuvir, ribavirin, or funds for purchasing Vosevi (sofosbuvir/velpatasvir/voxilaprevir) for retreatment.

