8.1.2.3 Sensitivity Analysis

As a sensitivity analysis, the percentage of subjects in the modified intention-to-treat-virologic-failure (VF) population (ITT population excluding those who did not achieve SVR₁₂ for reasons other than on treatment VF and relapse) achieving SVR₁₂, will be summarized.

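### Relapse closes at 12 weeks after the last dose with no visit window, but the only HCV RNA scheduled before week 24 may fall on days 70–98, so a relapse first seen late can drop out of the virologic-failure analysis

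*Protocol*

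**What the plan says.** **Relapse definition.** Protocol 8.1.2.2 lists "post-treatment relapse (defined as confirmed HCV RNA" at or above "LLOQ between end of treatment and 12 weeks after the last dose of study drug among subjects who completed treatment as planned". The subject must also be below LLOQ at end of treatment, and reinfection is excluded. Completion means at least 49 days of drug. The protocol spells out confirmation only in the on-treatment stopping rule (5.4.1.1), where it is "defined as 2 consecutive HCV RNA measurements".

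**Schedule.** In 5.1.6.1, "Visit 10 should occur 12 weeks after end of G/P treatment", with a tolerance of ± 14 days. The preceding contact is "Visit 9: Telephone encounter or in person visit (4 week after end of G/P treatment", and its listed activities include no blood draw. Table 5, footnote 3, agrees: "HCV RNA testing at V2, V4, V8, and V10 and V11 are study paid labs", with Visit 6 billed as standard of care. Visit 9 is not on the list.

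**Use of the classification.** Section 8.1.2.1 tabulates reasons for SVR12 non-response, giving on-treatment failure, relapse and other as examples. The sensitivity population in 8.1.2.3 (mITT-VF) removes ITT subjects who missed SVR12 "for reasons other than on treatment VF and relapse".

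**Elsewhere.** Section 5.5.1.1, on retreatment, describes relapse as "unquantifiable viral load after completion of treatment that during the post-treatment follow-up period becomes quantifiable", with no 12-week limit. Section 8.1 promises visit windows for the SVR endpoints and does not mention relapse. The SAP lists relapse as an outcome but gives no definition, no window and no mITT-VF analysis.

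**The concern.** The definition and the schedule do not fit together. The relapse interval ends on the target day of the one scheduled visit that could reveal a relapse, while that visit may take place up to 14 days later. No dated confirmatory draw is scheduled at all.

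A viremic subject first sampled after day 84 therefore fails SVR12, yet on the literal text is neither an on-treatment failure nor a relapse. The remaining label is the residual one, and 8.1.2.3 removes subjects with that label. An analysis meant to isolate virologic efficacy would then discard a virologic failure. Two results are at stake: the relapse percentage, which is one of the two secondary efficacy endpoints, and the mITT-VF SVR12 rate. With about 30 subjects, a single case decides whether any virologic failure is reported.

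**Working it through.** The plan states no figure that depends on this rule, so there is nothing to reproduce first.

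**Inputs**
- Relapse limit: 12 × 7 = day 84 after the last dose (8.1.2.2).
- Visit 10: 84 ± 14, so days 70 to 98; 98 − 70 + 1 = 29 permitted days (5.1.6.1, Table 5).
- Visit 11: 24 × 7 = 168, ± 28, so days 140 to 196 (5.1.6.1).
- Arm 1 size: 30 (5.1.5, 8.2).
- Assumptions: Visit 10 is spread evenly over its permitted days, and the lag to a confirmatory draw is 7 or 14 days. The documents give neither.

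**Step 1. Share of relapses first seen at Visit 10 that miss the definition**

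| Reading of 8.1.2.2 | Missed when Visit 10 is after | Share |
|---|---|---|
| First quantifiable value by day 84, confirmation at any time | day 84 | 14/29 = 48% |
| Both samples by day 84, lag 7 days | day 84 − 7 = 77 | 21/29 = 72% |
| Both samples by day 84, lag 14 days | day 84 − 14 = 70 | 28/29 = 97% |
| Visit 10 window applies, confirmation may follow | day 98 | 0/29 = 0% |

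Sensitivity to visit timing: on the first reading, any continuous distribution symmetric about day 84 gives 50%, and visits held on or before day 84 give 0%. With both samples required by day 84 and a 7-day lag, uniform, triangular and normal (SD 5 days) timing give 75% to 92%.

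**Step 2. Effect on mITT-VF**

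Let r relapses among 30 all miss the definition, with no other non-responders. ITT SVR12 is (30 − r)/30. With relapses kept, mITT-VF equals that figure. With them removed, it is (30 − r)/(30 − r). Intervals are two-sided 95% Wilson, with centre (p + z²/2n)/(1 + z²/n), half-width [z/(1 + z²/n)]·√(p(1 − p)/n + z²/4n²), and z = 1.96.

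| r | Relapses kept | Relapses removed |
|---|---|---|
| 1 | 29/30 = 96.7% (83.3–99.4%) | 29/29 = 100% (88.3–100%) |
| 2 | 28/30 = 93.3% (78.7–98.2%) | 28/28 = 100% (87.9–100%) |

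**Step 3. Does other text close the gap?**
- The windows in 8.1 are for SVR endpoints only, and the SAP supplies none.
- Table 5 has a treatment-failure row with HCV RNA, but without a date.
- A week-4 sample would help, and here the protocol disagrees with itself. Section 5.1 says the post-treatment visits evaluate SVR4, and 8.1.2.5 lists SVR4 as an endpoint. Section 5.1.5 bases the schedule on guidance that includes HCV RNA at post-treatment week 4. Table 5 and the Visit 9 text contain no such sample.

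**The case against.** The best defence is that the 12-week limit was never meant as exactly day 84. SVR12 in 8.1.2.1 is worded with the same bare 12 weeks, and nobody would score it only from samples drawn on that day. Section 8.1 attaches windows to the SVR endpoints, and reading relapse in the same way is natural; nothing is then lost. This is probably what the authors intended, but the text does not say so, and the SAP leaves it open.

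A reader might infer that most relapses would be lost, or that the relapse endpoint would sit near zero whatever the drug does. The documents do not support that. It requires the confirmatory sample to fall by day 84 as well, which 8.1.2.2 does not state, and the 72% and 97% figures rest on assumed lags. Standard-of-care HCV RNA results are also abstracted (5.1.6) and could reveal some relapses earlier.

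Two other inferences go too far. Subjects with 42–48 days of drug who are below LLOQ at end of treatment and then rebound fall outside both failure categories. Restricting relapse to treatment completers is nevertheless a defensible design choice, and the list of reasons in 8.1.2.1 is open-ended. Section 5.5.1.1 is not a rival endpoint definition: it governs retreatment, and 5.1.9 has failure confirmed before retreatment is given.

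It is also fair that the practical effect may be nil. If the 0.97% failure rate quoted in 5.5.8.1 for chronic infection applied here (an assumption), 30 × 0.0097 ≈ 0.3 failures would be expected. The chance of none would be 0.9903^30 ≈ 75%. A viremic subject under a residual label would still be visible in the table of reasons.

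**Conclusion.** The concern holds in a limited form. Followed literally, 8.1.2.2 does not count a relapse first detected on days 85–98, and 8.1.2.3 then removes that subject from mITT-VF. The share affected is 48% of Visit 10 detections under evenly spread visits when only the first sample must be in time. Across readings it runs from 0% to nearly 100%, and the documents do not settle which reading applies.

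One affected relapse in 30 moves mITT-VF SVR12 from 96.7% to 100%, provided there are no other non-responders. The damage is confined to the relapse percentage, the table of reasons and this one sensitivity analysis. A reader might suppose that the headline efficacy result is at risk. It is not, because the subject counts as a non-responder in the primary ITT analysis on any reading. The ambiguity should be removed before the data are analysed, because a single case changes the message.

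**What to change.** 1. In 8.1.2.2 and the SAP, define relapse as HCV RNA at or above LLOQ after end of treatment through the upper end of the SVR12 visit window (day 98). Say what confirmation means after treatment and allow it on a later sample. Retain the completer restriction and the reinfection exclusion.
2. In 8.1.2.3 and the SAP, state that a treatment completer whose SVR12 non-response is a quantifiable HCV RNA in that window stays in the mITT-VF denominator as a virologic failure, even if no confirmatory sample follows.
3. Report rebound after fewer than 49 days of drug as its own named reason for non-response.
4. Reconcile the relapse wording of 5.5.1.1 with 8.1.2.2. This concerns consistency of terms only; no view is taken on who should be retreated.
5. Reconcile Table 5, which has no HCV RNA at post-treatment week 4, with the SVR4 endpoint in 5.1 and 8.1.2.5.

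Items 1 to 3 cost a few sentences and need no extra visits or samples. The small downside is that the reported relapse count may be slightly higher and may include an unconfirmed value, which can be flagged in the table of reasons. Whether item 5 affects sampling depends on how the sponsor resolves it.

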8.1.2.3 Sensitivity Analysis

As a sensitivity analysis, the percentage of subjects in the modified intention-to-treat-virologic-failure (VF) population (ITT population excluding those who did not achieve SVR₁₂ for reasons other than on treatment VF and relapse) achieving SVR₁₂, will be summarized.

8.1.2.4 Subgroup Analysis

The percentage of ITT subjects with SVR₁₂ will be calculated, as will the corresponding two-sided 95% Wilson score intervals by the following subgroups:

- HCV GT
- Timing of HCV treatment initiation after transplant
- Study drug compliance

Further details about subgroup analyses will be described in the Statistical Analysis Plan

8.1.2.5 Additional Efficacy Endpoints

The following additional efficacy endpoints will be summarized for the ITT population:

- The percentage of subjects with HCV RNA < LLOQ at each post-baseline visit in the Treatment Period (using data as observed);
- The percentage of subjects with SVR4;
- The percentage of subjects with SVR24 and the concordance between SVR12 and SVR24

In the above analyses for SVR, the percentage of subjects and a two-sided 95% Wilson score interval will be summarized.

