Subjects who are transplanted with kidneys from HCV RNA-positive donors in Arm 1 will be followed for 1 year after the date of transplantation to evaluate SVR12, SVR24, safety, death, graft failure, acute allograft rejection, delayed graft function, ALT elevation >5 times the upper limit of normal, eGFR and proteinuria. Specifically, scheduled in-person visits for subjects who received organs from HCV RNA-positive donors in Arm 1 and receive G/P treatment will consist of day of transplant, Day 1 of G/P treatment, weeks 1, 2, 4, and 8 (planned end of treatment visit) after starting G/P. Additional scheduled visits will take place at Post Treatment Week 4, Post Treatment Week 12, Post Treatment Week 24 (e.g., post G/P treatment visits) to evaluate SVR4, SVR12 and SVR24 and 1 year post transplant. The post-transplant study visit schedule for MYTHIC has been designed such that these visits should take place on the same days as standard of care clinical visits. For subjects in Arm 1 study-objective pertinent data will be collected while awaiting a transplant (ie, SAEs, hospitalizations, delisting from waitlist, death), and post-transplant (ie, death, graft failure, acute allograft rejection, delayed graft function, eGFR, proteinuria, ALT elevation >5 times the upper limit of normal, and SAEs). Subjects who experience virologic failure in

Arm 1 will be evaluated for the emergence/persistence of DAA-resistant viral variants, and suitable retreatment will be offered.

Study visits in Arm 2A will take place at weeks 1, 4, 8, 12, and 24 weeks after transplantation. Safety, graft survival, mortality, allograft rejection, and results of HCV RNA testing will be captured for a period of 24 weeks post-transplant. Study-objective pertinent data will be collected while awaiting a transplant (i.e., SAEs, delisting from waitlist, death), and post-transplant (i.e., death, graft failure, acute allograft rejection, delayed graft function, eGFR, proteinuria, ALT elevation >5 times the upper limit of normal, and SAEs). For subjects of Arm 1 and Arm 2A who become HCV infected, we will collect additional clinical outcomes of sclerosing cholestatic hepatitis and extrahepatic manifestations of HCV.

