Efficacy and safety outcomes assessments recorded in the medical record as part of the subject's standard clinical management and follow up will be submitted using electronic CRFs where available in the medical record, except for protocol defined central laboratory assessment collection, drug dispensation and accountability, and required monthly medical record source record verification/submission. The central laboratory will be at MGH.

The schedule of procedures for the study regarding the treatment of HCV infection for recipients of HCV RNA-positive kidneys in Arm 1 ([Table 5](#)) is more intense but principally based on the AASLD guidelines²⁶ for the treatment of HCV, which recommends:

1) Baseline: hepatic fibrosis assessment, drug-drug interaction assessment, hepatitis B serologies (HBs Ag, anti-HBc, anti-HBs, reflex HBV DNA if anti-HBc-positive),

CBC/platelets, hepatic function panel, and estimated glomerular filtration rate (eGFR, done in this study using the MDRD equation);

2) On treatment monitoring: HCV RNA and routine CBC/platelets, hepatic panel and eGFR) are recommended at week 4 and as clinically indicated;

3) Post-treatment monitoring: HCV RNA and routine labs are recommended at 4 and 12 weeks post-treatment.

In Arm 1, G/P dosing in Arm 1, treatment/side effect management, and duration will be recorded in the study CRFs by the site PI and or clinical provider designee and managed according to the AASLD guidelines, center standard of care, with additional assessments required by the protocol according to the Study Activities table ([Table 5](#)).

The schedule of procedures regarding kidney transplantation activities is based on the local center's practice for kidney transplant care.

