8.1 Statistical and Analytical Plans

The data analysis will be generated using SAS version 9.4 or higher for windows and/or STATA software version 14.0 or higher (StataCorp LP, College Station, TX). SAS Institute Inc. SAS and all other SAS Institute Inc. product or service names are registered trademarks or trademarks of SAS Institute Inc., Cary, NC, USA. All statistical tests (if applicable) and confidence intervals will be two-sided with an alpha level of 0.05.

Descriptive statistics will be provided, such as the number of observations (N), mean, and standard deviation (SD) for continuous variables and counts and percentages for discrete variables.

The efficacy and safety of the “reactive” G/P treatment of patients who become HCV RNA-positive after receiving a kidney from a study eligible HCV RNA-negative/HCV Ab-positive donor in Arm 2A are not an objective of this study, and they are not included in assessments of efficacy or safety described below. The time to transplant and clinical outcomes and data post-transplant from patients in Arm 2A are included in those secondary endpoints.

The primary analysis will occur after all recipients of HCV RNA-positive kidneys in Arm 1 have completed post-treatment week 12 visit (corresponding to SVR₁₂ data collection) or prematurely discontinued study. The primary analysis of SVR₁₂ will be performed on the intention-to-treat (ITT) population defined as all enrolled subjects who received a study eligible HCV RNA-positive kidney and received at least one dose of G/P according to actual treatment received (Arm 1).

No data will be imputed for any efficacy or safety analysis except for analyses of SVR endpoints (HCV RNA data). HCV RNA values will be selected for the analyses of all SVR endpoints (e.g., SVR₄ and SVR₁₂, SVR₂₄) based on defined visit windows. A backward imputation method will be used to impute missing responses for SVR analyses. Additional details of analyses to be performed will be specified in the Statistical Analysis Plan.

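### SVR4 is a listed endpoint, but no HCV RNA is scheduled at post-treatment week 4; under the stated backward imputation it would largely repeat SVR12

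*Protocol*

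**What the plan says.** **Endpoint.** Protocol 8.1.2.5 includes "The percentage of subjects with SVR4" for the ITT population (Arm 1), with a two-sided 95% Wilson interval. Section 5.1 says the post-treatment visits are held "to evaluate SVR4, SVR12 and SVR24 and 1 year post transplant".

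**Sampling.** Section 5.1.6.1 describes the week-4 contact as "Telephone encounter or in person visit (4 week after end of G/P treatment"). Its activities are adverse events, medication data and confirmation of later visits. Visits 10 and 11 each list research phlebotomy; Visit 9 does not. Table 5, footnote 3 states: "HCV RNA testing at V2, V4, V8, and V10 and V11 are study paid labs". It adds that the Visit 6 test is billed as standard of care. Visit 9 is in neither group. Section 5.3.1.1 makes Tables 4 to 6 the source for when HCV RNA is drawn.

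**Missing data.** Section 8.1 names SVR4 among the SVR endpoints and says: "A backward imputation method will be used to impute missing responses for SVR analyses". It refers to visit windows and leaves further detail to the SAP. The SAP summary has rows for SVR12, virologic failure and post-treatment relapse. It mentions neither SVR4, nor windows, nor imputation.

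**The concern.** The sections that define the endpoint assume a week-4 measurement, and the sections that govern sampling do not provide one. Normally such an endpoint could simply not be estimated, and the gap would be obvious. Here the imputation rule fills it without any signal: the next scheduled value after Visit 9 is the Visit 10 sample, which is the SVR12 sample itself.

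An SVR4 rate printed with its own interval would then look like a separate measurement that agrees with SVR12, while holding little or no week-4 information. Section 8.1.2.5 limits the on-treatment HCV RNA summary to observed data but sets no such limit for SVR4.

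**Working it through.** The documents give no SVR4 figure to reproduce. The check therefore compares the schedule with the endpoint, follows the imputation rule through, and shows the effect at n = 30.

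**1. Scheduled HCV RNA around post-treatment week 4 (Arm 1)**

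| Visit | Time | HCV RNA scheduled? | Source |
|---|---|---|---|
| V8 | End of treatment, ±7 days | Yes | Table 5, footnote 3 |
| V9 | Post-treatment week 4, ±7 days | No | Footnote 3; 5.1.6.1 |
| V10 | Post-treatment week 12, ±14 days | Yes (SVR12) | Footnote 3 |
| V11 | Post-treatment week 24, ±28 days | Yes (SVR24) | Footnote 3 |

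This rests on footnote 3 and the visit text, because the tick columns of Table 5 are not reliable in the text copy.

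**2. Backward imputation.** Assumed rule: a missing response takes the next later available value, and a subject with no later value is a non-responder. Without a week-4 sample:

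- SVR4 = V10 if present; otherwise V11; otherwise non-response.
- SVR12 = V10 if present; otherwise V11; otherwise non-response.

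The two definitions are the same. V10 and V11 can each be below LLOQ, at or above LLOQ, or missing, which gives 3 × 3 = 9 patterns. SVR4 differs from SVR12 in 0 of 9.

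Now suppose a week-4 value exists, so that there are 2 × 9 = 18 patterns. SVR12 is a response in 4 of the 9 week-12/week-24 patterns: three with V10 below LLOQ, and one with V10 missing and V11 below LLOQ. It is a non-response in the other 5. A week-4 value below LLOQ disagrees with SVR12 in 5 patterns, and a value at or above LLOQ disagrees in 4. The total is 5 + 4 = 9 of 18. These are counts of possible patterns, not probabilities; they show only that a real week-4 sample would carry its own information.

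**3. Illustration at n = 30.** Suppose all 30 subjects are below LLOQ at week 4, none has a week-4 sample, and k relapse between weeks 4 and 12. The Wilson limits are

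[p + z²/2n ± z√(p(1−p)/n + z²/4n²)] / (1 + z²/n), with z = 1.96 and n = 30.

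| k | SVR4 if measured | SVR4 as imputed (= SVR12) |
|---|---|---|
| 0 | 30/30 (88.6% to 100%) | 30/30 = 100% (88.6% to 100%) |
| 1 | 30/30 (88.6% to 100%) | 29/30 = 96.7% (83.3% to 99.4%) |
| 2 | 30/30 (88.6% to 100%) | 28/30 = 93.3% (78.7% to 98.2%) |
| 3 | 30/30 (88.6% to 100%) | 27/30 = 90.0% (74.4% to 96.5%) |

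The values of k are illustrative. Each relapse between weeks 4 and 12 moves the imputed SVR4 down by one subject. With no such relapse, the two figures agree whether or not anything was measured at week 4.

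**The case against.** **Week-4 values may exist.** Section 5.1.5 says Arm 1 is managed by the guideline and center standard of care, with Table 5 adding to that, and it summarises the guideline as: "Post-treatment monitoring: HCV RNA and routine labs are recommended at 4 and 12 weeks post-treatment". Section 5.1.6 has sites abstract HCV RNA obtained in routine post-treatment care. A reader might infer that every SVR4 value must be a copy of SVR12. The documents do not support that: a subject with a routine or failure-triggered week-4 sample would have a true SVR4. What remains is that the protocol does not require such a sample, and footnote 3 names only Visit 6 as a standard-of-care HCV RNA test.

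**The rule is not defined.** Section 8.1 gives neither the carry rule nor its limits, so the 0-of-9 result depends on the plain reading used above. This stands as a caveat, and also as a reason to write the rule down.

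**SVR4 may not be reported.** The SAP has no SVR4 row, and the only concordance planned in 8.1.2.5 is SVR12 with SVR24. But the SAP is a draft summary, and its silence does not remove an endpoint from the protocol.

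**Relapse.** A reader might also infer that relapse is miscounted or found late. At target dates, dosing on days 3 to 58 puts week 4 at day 58 + 28 = 86 and week 12 at day 58 + 84 = 142, which is 8 weeks apart. The visit windows make that gap anywhere from 10 − 5 = 5 to 14 − 3 = 11 weeks. But section 8.1.2.2 counts relapse cumulatively from end of treatment to 12 weeks after the last dose, and nothing here shows that the count changes. When relapse is detected is a matter of patient monitoring, not of this analysis.

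**Conclusion.** The inconsistency is confirmed: 8.1.2.5 and 5.1 call for SVR4, while 5.1.6.1 and Table 5, footnote 3 schedule no sample for it. If a missing value takes the next later one, SVR4 equals SVR12 for every subject without an off-schedule or failure-triggered week-4 HCV RNA. The share of such subjects can be as high as 100% of Arm 1, but the documents do not allow it to be estimated. The reported rate and interval would then carry little or no week-4 information.

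Severity is minor. SVR4 is neither the primary nor a secondary endpoint, and the stopping rule in 5.4.2 does not use it. The result for SVR12 is unchanged.

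**What to change.** Choose one of the following:

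- **Delete SVR4** from 8.1.2.5 and 5.1, and remove the mention in 8.1.
- **Keep SVR4 on observed data only.** Report it for subjects with an HCV RNA in a stated week-4 window, give that denominator, and do not impute from Visit 10 while Visit 9 has no scheduled sample.

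In either case, make 5.1, 5.1.6.1, Table 5 and 8.1.2.5 agree, and state in the SAP the visit windows and the exact backward rule for the SVR endpoints that remain.

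Either option costs a line or so of wording. The downside is that SVR4 is lost, or rests on a smaller and possibly selected group, since subjects tested off schedule may differ from the rest.

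Scheduling an HCV RNA at Visit 9 is optional. It would make SVR4 a real measurement, but Visit 9 may now be a phone call, so it would need a lab or in-person visit for about 30 subjects. Once that sample is scheduled, imputing an occasional missed draw from a later result is defensible, and a blanket ban is not needed.
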